 - Change in self-reported (questionnaire) clinical symptom onset in tobacco users, marijuana smokers, or vapers. A symptom checklist will include: cough, runny nose, scratchy/sore throat, fever, chills, fatigue, muscle ache, shortness of breath, diarrhea/nausea/vomiting, loss of taste/smell, and red /painful eye (Time Frame: Baseline to 4 weeks)
 - Change in healthcare utilization and hospitalization in tobacco users, marijuana smokers, or vapers (Time Frame: Baseline to 4 weeks)

Participant timeline {13}

Study participants will remain in the trial for 4 weeks. After completing the intervention, they will be followed up for the next 11 months via text messaging to ask about clinical symptoms and healthcare utilization, experience using mouthwash, and their interest in using mouthwash after the trial.

Sample size {14}

A total of 150 eligible individuals will be enrolled in the trial after providing informed consent and randomly assigned to 1 of 5 groups. This trial is sized to provide precise estimates of effect size for a future definitive trial with at-risk individuals. However, this trial would be able to detect a rather large effect: a sample size of 24 for a mouthwash group and 24 for the distilled water control group is estimated to have 80% power to detect a 2-fold difference in mean values between the 2 groups with a 2-sided alpha=0.05. Assuming 80% retention through 28 days, 30 participants per group at baseline (150 total) will be enrolled.

Recruitment {15}

Two recruitment routes have been planned for this trial:

1- Upon referring to testing centers at UCSF individuals will receive the trial details via a letter or flyer, and if tested positive for COVID-19, they will contact study staff and enroll into the trial.

2- The UCSF Clinical and Translational Science Institute (CTSI) Participant Recruitment Program (PRP) provides new COVID+ patient lists enabling us to contact COVID+ patient who are interested in participating in research studies.

After study staff confirm their eligibility, participants will receive the sample collection package and written instructions at their home along with scheduling a videoconference to collect saliva samples and use the assigned mouthwash during the 4-week period.

Assignment of interventions: allocation

Sequence generation {16a}

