The permuted block allocation sequence stratified on language (English/Spanish) will be generated in SAS and uploaded to REDCap to randomly assign participants to one of the five mouthwash groups.

Concealment mechanism {16b}

The randomization will be concealed in REDCap; once participant's eligibility is confirmed, consent form is signed, and the baseline questionnaire completed, then the assignment is revealed. No study staff involved in recruitment or procedures with participants or participants know the allocation sequence since it is revealed via REDCap after qualifying steps.

Implementation {16c}

Following release of the REDCap allocation sequence for an individual participant, study staff will obtain the relevant kit and deliver to participants.

Assignment of interventions: Blinding

Who will be blinded {17a}

Participants will be blinded/masked to the extent possible by covering product labels, but the solutions have different colors, flavors, and smells so they may guess which group they have been assigned. Lab staff performing assays (outcome assessors) and data analysts will be blinded/masked to intervention group.

Lab staff will receive participants' samples with barcode stickers with only the study ID number. The data analyst will receive data set with coded group identifier.

Procedure for unblinding if needed {17b}

We will not unblind the study groups for outcome assessors unless subsequent actions to assure participants' safety would be affected.

Data collection and management

Data will be collected via various questionnaires (eligibility, baseline, daily and long-term follow ups) designed in REDCap. The data collection will be supervised and assessed regularly for completeness and inconsistencies.

Plans for assessment and collection of outcomes {18a}

We have designed questionnaires (eligibility, baseline, daily and long-term follow ups, sample collection, and RT-PCR results) in REDCap to collect data from participants and assess outcomes. We will train research and lab staff regarding each related steps and data collection. We have pilot tested assessments. The data collection will be supervised and assessed regularly for discrepancies.

Plans to promote participant retention and complete follow-up {18b}

We have planned to send daily reminders to participants to use their assigned mouthwashes and follow-up the next day to see if they have used it and if there were problems.

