At any time during the trial, if a participant discontinues from the study or deviates from intervention protocols, we will record the information.

Data management {19}

We have planned to use unique barcodes on sample collection kits and participants' packages to be scanned during the trial and automatically recorded in an Excel file on a UCSF secured laptop and the Cloud. Only PIs know about the codes. [name] (SB) will supervise data entry and its quality on a regular basis. Data will be linked to a REDCap form.

Confidentiality {27}

Email address and telephone number are the only personal identifying information which will be kept confidential in REDCap on UCSF secured servers. Participant information will be kept confidential. After the study and its follow-up in 12 months is finished, email address and phone number will be deleted.

Plans for collection, laboratory evaluation and storage of biological specimens for genetic or molecular analysis in this trial/future use {33}

The study procedures include collecting saliva and oropharyngeal samples from participants on 3 study days (day 1, 7, 28), assaying them, and storing them for future potential research use.

Statistical methods

Statistical methods for primary and secondary outcomes {20a}

Primary outcome measure: To assess and compare the SARS-CoV-2 viral load in unstimulated saliva and throat wash (gargle lavage) samples at baseline, days 7 and 28, we will compare the viral load (cycle threshold, Ct) among active groups versus the control (water) and within groups on day 28 using proportional hazards regression models with right censoring for undetermined Ct, stratifying on replicate for a marginal repeated measures survival model.

We follow the intention-to-treat (ITT) approach for efficacy analyzing participant data asrandomized; a safety analysis will tabulate any adverse experiences. The ITT group will include participants who are randomized after meeting the eligibility criteria and receive at least one study mouthwash dose and have PCR data from collected samples. A safety analysis group will include participants who received study mouthwashes and have safety evaluation data after using the mouthwash at least once.

Interim analyses {21b}

We plan to conduct an interim analysis after 10 participants in each group (N=50) have finished the 28-day period (using mouthwash). The alpha-spending approach with an O'Brien-Fleming stopping rule will be used.

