Plans for communicating important protocol amendments to relevant parties (e.g. trial participants, ethical committees) {25}

Study PIs will communicate with the UCSF ethics committee (institutional review board) before making any modifications during the study.

Dissemination plans {31a}

We plan to disseminate study results via publications. (If the interim analysis shows important early findings, we will share that information with the health research community via preprint such as MedRxiv.) We will report aggregate study results to ClinicalTrials.gov for the public.

Discussion

This clinical trial was originally designed to be conducted in-person at the UCSF School of Dentistry to collect saliva samples, but since specific settings and supplies are required to examine COVID positive patients in-person, we were instructed to modify the study protocol so participants could receive sample collection kits in their homes and staff instruct them via videoconference software, telephone, and written instructions to guide them through the process.

Abbreviations

SARS-CoV-2: Severe Acute Respiratory Syndrome- CoronaVirus-2

COVID-19: Corona Virus Disease-2019

Declarations

• Acknowledgments

The authors are grateful for the support from [name], [name], and [name] for preparing for this trial.

• Authors' contributions

SB conceived and conceptualized the idea, designed the study, prepared the UCSF IRB and ClinicalTrials.Gov application and developed study documents, contributed in preparing the budget, applied for funding, developed study logistics, prepared presentations, and drafted the protocol. SG contributed to conceptualization and study design, the UCSF IRB and ClinicalTrials.Gov application and developing study documents, prepared the budget, applied for funding and prepared contracts to receive the funding, contributed to study logistics, and edited this protocol. They both read and approved the final protocol.

- Funding
 - T32DE007306 (National Institute of Health (NIH)/National Institute of Dental and Craniofacial Research (NIDCR) supports SB during the study)

- U01DE025507-S1 (National Institute of Health (NIH)/National Institute of Dental and Craniofacial Research (NIDCR) supports some clinical trials coordinating center assistance)
- R00RG2901 (University of California Office of President (UCOP) Emergency
 COVID19 Research Funding: California Breast Cancer Research Program
- Rowpar Pharmaceutical Inc.

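### Interim results may be preprinted if they seem important, a trigger not stated to be tied to the O'Brien-Fleming rule or to enrolment having stopped

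*Combined protocol and SAP*

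**What the plan says.** Interim analyses {21b} schedules one look: "We plan to conduct an interim analysis after 10 participants in each group (N=50) have finished the 28-day period". For that look it adds: "The alpha-spending approach with an O'Brien-Fleming stopping rule will be used". It gives no numerical boundary and no information fraction, and it does not name the specimen or comparison to be tested.

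Dissemination plans {31a} then says, in a parenthesis: "If the interim analysis shows important early findings, we will share that information with the health research community via preprint". What counts as important is not defined. No section makes release depend on the boundary, pauses enrolment for the interim, or keeps by-arm interim results confidential.

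Four other parts of the protocol bear on this:
- Who will be blinded {17a}: product labels are covered, but the rinses differ in colour, flavour and smell, "so they may guess which group they have been assigned". Laboratory staff and the data analyst are blinded.
- Intervention description {11a} and Outcomes {12}: all four active rinses are over-the-counter products, and symptoms are a self-reported secondary outcome.
- Composition of the data monitoring committee {21a}: it lists only the PI and co-PI, who also form the steering committee {5d}.
- Sample size {14}: the trial is meant to estimate effect sizes for a later definitive trial.

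**The concern.** A stopping rule says when interim evidence is strong enough to act on. A release rule says when it may be made public. The protocol has the first, in outline, and leaves the second to an undefined word. The two people who would judge importance also run the trial.

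If a result short of the boundary were released, the trial would carry on with its by-arm estimates in public view. A participant who believes they have water could read which product looks better and buy it. Other mouthwashes are prohibited {11d}, but the adherence check described is a daily self-report {11c}. Participants could also use the assigned rinse more or less diligently, drop out, or report symptoms differently. Outside readers would see an estimate from 10 per arm, picked out because it was striking. That works against the aim of giving reliable effect sizes to a future trial.

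**Working it through.** **1. The plan's own figures.** Sample size {14} takes "a sample size of 24 for a mouthwash group and 24 for the distilled water control group" as giving "80% power to detect a 2-fold difference in mean values between the 2 groups with a 2-sided alpha=0.05", and then: "Assuming 80% retention through 28 days, 30 participants per group at baseline (150 total) will be enrolled". Check: 24 / 0.80 = 30 per group and 5 × 30 = 150. This reproduces. The 24 cannot be checked independently because no SD is given.

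**2. How many could still be enrolled.** Fifty completers at 80% retention imply 50 / 0.80 = 62.5, about 63 randomised. 150 − 63 = 87. This is an upper figure: no accrual rate is given, and recruitment during the 28-day lag would lower it.

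**3. Implied SD (assumption).** Read the 2-fold difference as 1 unit on the log2 scale. Then SD = 1 / [(1.960 + 0.842) × √(2/24)] = 1.24 log2; the t-test version gives 1.21.

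**4. Precision at the interim.** SE = 1.24 × √(2/10) = 0.55 log2. The 95% interval is the estimate multiplied or divided by 2^(1.96 × 0.55), about 2.1 (2.2 with the t quantile on 18 df). At 24 per arm the factor is about 1.6. If the SD were 1.0 the interim factor would be 2^(1.96 × 0.447), about 1.8; if it were 2.0, 2^(1.96 × 0.894), about 3.4.

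**5. O'Brien-Fleming-type level at the interim.** The information fraction t is 10/24 = 0.42 (evaluable) or 10/30 = 0.33 (enrolled). Two versions of the spending function:
- Two-sided: 2[1 − Φ(1.960/√t)].
- Per side: 4[1 − Φ(2.241/√t)].

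| t | Two-sided version | Per-side version |
|---|---|---|
| 10/24 | p = 0.0024, z = 3.04 | p = 0.0010, z = 3.28 |
| 10/30 | p = 0.0007, z = 3.39 | p = 0.0002, z = 3.71 |

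**6. Chance of a false signal.** Four null comparisons share one water arm, with 10 per arm and one specimen. Simulated chance that at least one passes:

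| Threshold (two-sided p) | At least one of four |
|---|---|
| 0.05 (illustrative trigger) | about 15.5% |
| 0.0024 | about 0.9% |
| 0.0010 | about 0.4% |
| 0.0002 | about 0.1% |

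These figures do not depend on the SD.

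**7. Selection at a true 2-fold effect.** With SD 1.21-1.24 and 10 per arm, nominal p<0.05 is reached about 40-42% of the time by t-test. The mean log2 estimate among significant results in the right direction is about 1.5, and 2^1.5 is about 2.8-fold.

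**The case against.** The strongest reply is that the parenthesis refers to the interim analysis, and the only decision rule for that analysis is O'Brien-Fleming, so an important finding may simply mean a crossed boundary. The text neither links nor separates the two, so it cannot be said that the plan deliberately sets a second trigger. What stands is that the link is not stated.

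A reader might infer that the boundary cannot be what is meant, because it is almost never crossed at 10 per arm. That holds only for null or modest effects. With SD 1.21, the chance of p<0.001 in one comparison is about 4% at a true 2-fold effect, but about 44% at 4-fold and 92% at 8-fold. The documents do not settle what was meant.

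A reader might also infer that a preprint short of the boundary breaks the trial's error control. It does not: posting an estimate spends no alpha and leaves the final critical value unchanged. The risk is to trial conduct and to how outsiders read the estimate.

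Three numerical readings also go too far:
- 150 − 50 = 100 participants left ignores the 80% retention.
- A significant interim result need not exceed 2.2-fold. The t-test uses the observed SD, and at a true 2-fold effect about 13-15% of significant results fall below that value. The exaggeration is an average.
- The 15.5% is not the plan's error rate, because nominal p<0.05 is not the plan's trigger.

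Some protection exists: the primary outcome is RT-PCR, and laboratory staff and the analyst are blinded. This is also a pilot, and quick sharing in a pandemic has value. These points limit the harm, but they do not address what participants and their study contacts would do after reading by-arm results.

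**Conclusion.** The gap is real. Following the protocol as written permits a comparative preprint from 10 per arm while the trial is running, with participants only partly blinded and the PI and co-PI as the only monitors described. Up to about 87 of 150 participants could still be unenrolled, given 80% retention and no stated accrual rate. Continued enrolment is an inference, though a fair one, since the target is 150 and no pause is described.

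The possible effects on adherence, use of other rinses, retention and symptom reports cannot be sized from the documents. The contrast between about 15.5% and 0.1-0.9%, and the average of about 2.8-fold, are illustrations. They rest on a nominal p<0.05 trigger and t-tests, and the 2.8-fold also on an SD of 1.21-1.24 log2. The plan states none of these, and its analysis is proportional hazards on censored Ct. The point should be corrected, but it does not undermine the validity of the final test.

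**What to change.** Replace the parenthesis in Dissemination plans {31a} with:

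*Comparative interim efficacy results will be released before the final analysis only if the prespecified O'Brien-Fleming boundary is crossed and enrolment has been stopped; otherwise no by-arm interim efficacy result will be shared beyond those conducting the interim analysis and the PIs until enrolment and day-28 follow-up are complete. Safety reporting and reporting to the IRB are not restricted.*

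For this to work, Interim analyses {21b} should state the numerical boundary and the comparison and specimen to which it applies. The wording names the PIs because section {21a} provides no separate monitoring body, and it is limited to efficacy so that an adverse-event imbalance can still be reported. The change costs a few lines of text and no participants. Its downside is that a suggestive result short of the boundary is published later; a result that crosses it and stops enrolment can still be preprinted at once.
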